#### Imputation Rules for Partial Therapy Dates

	Missing	Impute	Exception
Therapy Examination* Date	Day	15	Default to the Randomization date if the imputed date is before the Randomization date. Default to the EOS date if the imputed date is after the EOS date
	Day /Month	Visit due date or 1 st July	
Primary Surgery Date	Day	15	
	Day /Month	1 st July	
AI Start Date	Day	1	Default to the Randomization date if the imputed date is before the Randomization date.
	Day /Month	01JAN	
AI End Date	Day	Last day of the month	Default to the Randomization date if the imputed date is before the Randomization date. Default to the EOS date if the imputed date is after the EOS date
	Day/Month	31DEZ	

#### Imputation Rules for Follow Up and End of Study Dates

	Missing	Impute	Exception
Follow Up Examination Date	Day	15	Default to the EOS date if the imputed therapy stop date is after the EOS date
	Day /Month	Follow up visit due date window lower bound	Default to the EOS date if the imputed therapy stop date is after the EOS date
End of Study Date	Day	15	10,5 Years after Randomization Date if the imputed date is after the EOS date
	Day /Month	10,5 Years after Randomization Date	

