7.3. Follow-up

After the therapy is complete, follow-up examinations are carried out at 36, 48 and 60 months in Arm A analogously to the therapy examinations in the Arm B. After the 60th monthly visits, the standardised follow-up examinations are carried out at yearly intervals (+/- 6 months) over a period of 5 years for both arms.

1. Physical examination
2. Bilateral mammogram (unilateral mammogram in the case of mastectomy)
3. Serious adverse events (see 9.1 and 9.2.4)

Affected protocol point:

- 1.2. Flow chart (page 12)

Old text:

1. Separate specification for patient history and clinical examination
2. No detailed information for gynaecological examination

Amended text:

1. Change to physical examination
2. Gynaecological examination with asterisk * in screening: * Including ultrasound (exception: status post hysterectomy) or ** at the therapy visits: ** "Follow-up examination in accordance with the current state of scientific knowledge"

Justification for the amendment:

- Points 9a–9f in the inclusion criteria are handled in a separate point (i.e. Amendment in point 1 "Patient selection" or additional point 5.4 "Diagnosis") (reason: The above-mentioned examinations from point 9 are not actual inclusion criteria but rather constitute guidelines for how inclusion criteria 3 and 4 are should be ensured.)
- Change of description in the exclusion criteria: "Manifest secondary malignancy or status post secondary malignancy between the time of initial diagnosis and randomisation" to "manifest secondary malignancy or status post secondary malignancy" (reason: misleading description; there are patients who were included status post secondary cancer who had to be set to ineligible.)
- The gynaecological examination at screening has been supplemented by a mandatory ultrasound examination (reason: accurate clarification of any pathological changes which otherwise could be attributed to the study medication is possible at inclusion.)
- The time frame for the gynaecological examination is extended to 6 months (reason: it is not feasible to obtain findings in a time frame of one month prior to randomisation.)

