### 3.1.2.2. Partial dates

Partially incomplete dates (day or day/month missing) will be imputed for dates of progression as well as for therapy begin and/or end dates. Completely missing dates and missing years will not be imputed.

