#### *Evaluation of censoring date for DFS analysis*

In case of no events and no early study termination, patients will be censored after 10.5 years. The last DFS event free day is evaluated as the maximum of the last treatment visit date and last follow up visit date including only visits with cancer status evaluation. In case of follow-up visits with documented cancer status but without a documented visit date, the lower bound of the due visit date window will be used. Follow-up visits with information whether patient is alive but without cancer status evaluation will not be used.

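### For a follow-up visit with only the year recorded, the SAP's literal rule uses the lower bound of the visit window and does not tie the date to that year; the end-of-study cap in the same row tests the wrong variable

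*SAP*

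**What the plan says.** SAP 3.1.2.2 limits imputation to dates that lack the day, or the day and month: "Completely missing dates and missing years will not be imputed". Any date handled in the tables that follow therefore has a recorded year.

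- **Follow-up visits, day and month missing** (table of rules for follow-up and end-of-study dates): "Follow up visit due date window lower bound". The exception attached to the follow-up row reads "Default to the EOS date if the imputed therapy stop date is after the EOS date".
- **Therapy visits, day and month missing** (table for partial therapy dates): "Visit due date or 1 st July". The text does not say when each option applies. The row label carries an asterisk whose footnote is not in the text available for this review.
- **Event, death and fracture dates, day and month missing** (table for partial progression dates): 1 January, so the recorded year is kept.

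The window comes from Protocol Amendment 1, section 7.3: "standardised follow-up examinations are carried out at yearly intervals (+/- 6 months) over a period of 5 years for both arms". The lower bound is thus 6 months before the due date.

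The imputed date reaches the primary analysis through the paragraph on DFS censoring in SAP 3.5.2: "The last DFS event free day is evaluated as the maximum of the last treatment visit date and last follow up visit date", counting only visits with a cancer-status evaluation. That paragraph also covers a visit with cancer status but no date at all: "without a documented visit date, the lower bound of the due visit date window will be used".

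**The concern.** The follow-up rule supplies a complete date from the visit schedule, although the year is the one part of the date that the site did record. Take a visit due on 1 March 2013 and entered only as 2013. The rule dates it 1 September 2012, which the CRF shows to be false. The SAP treats this visit exactly as it treats a visit with no date.

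The exception in the same row does not protect the variable being imputed. It tests a therapy stop date, which the therapy table already limits to the end-of-study date. A follow-up visit with only the day missing is set to the 15th, and can then fall after an end-of-study date earlier in that month with nothing to pull it back.

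At stake is the censoring date of event-free patients, and with it the number at risk in the late part of the DFS curve. No event is moved by this rule.

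**Working it through.** The documents give no figure for this point, so there is nothing of theirs to reproduce.

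**Inputs**

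- Window: due date D plus or minus 6 months, so lower bound L = D − 6 months (Protocol Amendment 1, 7.3).
- True visit date T = D + x, with x between −6 and +6 months. The distribution of x is an assumption, varied below.
- Due dates spread evenly over the calendar year (assumption).
- Share of visits with only the year recorded: not stated.

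**Step 1: time lost under the literal rule.** Loss V = T − L = x + 6 months, so the mean loss is 6 + mean(x).

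**Step 2: chance of a wrong year.** With due dates even over the year, an interval of V months (at most 12) crosses 1 January with probability V/12. So P(wrong year) = mean(V)/12. For visits centred on the due date this is 6/12 = 50%.

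**Step 3: how much comes from ignoring the year.** Compare with the later of L and 1 January of the recorded year. The loss is then min(V, m), where m is the time from 1 January to T, uniform on 0 to 12 months and independent of V. Its mean is mean(V) − mean(V²)/24, so the floor saves mean(V²)/24.

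- All visits on the due date: V = 6, saving 36/24 = 1.5 months.
- Even over the window: mean(V²) = 48, saving 48/24 = 2.0 months.
- All late (x from 0 to +6): mean(V²) = 84, saving 84/24 = 3.5 months.
- All early (x from −6 to 0): mean(V²) = 12, saving 12/24 = 0.5 months.

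| Visit timing (assumed) | Wrong year | Mean loss, literal rule | Mean loss with 1 January floor | Saved by the floor |
|---|---|---|---|---|
| On the due date | 50% | 6.0 months | 4.5 months | 1.5 months |
| Even over ± 6 months | 50% | 6.0 months | 4.0 months | 2.0 months |
| All late, 0 to +6 months | 75% | 9.0 months | 5.5 months | 3.5 months |
| All early, −6 to 0 months | 25% | 3.0 months | 2.5 months | 0.5 months |

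A simulation of 2,000,000 visits per row gave the same values.

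**Step 4: the other possible reading.** If the rule means keep the year and take only day and month from the lower bound, the mean loss is 0. Single errors then reach 6 months either way when visits fall on the due date, and almost 12 months either way when visits fill the window.

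**Step 5: illustrative size.** Assume that 2 to 10% of last event-free visits are year-only and that mean follow-up from year 2 is 5 to 7 years; neither figure is in the documents. The literal rule then understates event-free time by 0.5 × 0.02 / 7 = 0.14% to 0.5 × 0.10 / 5 = 1.0%. The part due to ignoring the year, 1.5 to 2 months with visits centred on the due date, is (1.5/12) × 0.02 / 7 = 0.04% to (2/12) × 0.10 / 5 = 0.33%.

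**Step 6: the end-of-study cap.** With only the day missing, the overshoot is at most 14 days (end of study on the 1st, visit set to the 15th). With day and month missing, the lower bound passes end of study only if end of study precedes the opening of the window.

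**The case against.** The strongest reply is that the SAP nowhere says the recorded year is dropped. Most entries in the three tables fill only the missing parts of a date, and the follow-up entry could be read the same way. That reading is possible, but the literal one is more likely. The lower bound is a complete date, the neighbouring end-of-study rule also gives a complete date (10.5 years after randomisation), and the censoring paragraph uses the same bound when no date exists. Under either reading the SAP should say what happens to the year.

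Second, the lower bound is a deliberate and consistent convention that avoids crediting event-free time nobody documented. This stands. A reader might infer that ignoring the year causes the whole 6-month loss, but the table above shows that most of it comes from the convention. Moving to a midpoint would be a matter of preference.

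Third, a reader might infer that the event rate is inflated because censoring dates move early while event dates do not. The documents do not support this. Year-only event and death dates go to 1 January, which is also about 6 months early on average if events are spread over the year.

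Fourth, the scope is narrow. The lower-bound rule covers follow-up visits only, and time is lost only at the last cancer-status visit of a patient without a DFS event. For therapy visits, 1 July always stays in the recorded year. The due-date option leaves it in 0% of cases (visits on the due date) to 25% (visits even over the window), but the text does not say when that option is used.

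Fifth, the edit checks, queries, source data verification and form locking in Amendment 2, section 11, should keep year-only dates few.

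Finally, a reader might infer a bias between arms, because Amendment 1, section 7.3, calls the visits at 36, 48 and 60 months follow-up in Arm A and therapy visits in Arm B. The documents do not show that the eCRF applies the two date rules along those labels, so no such bias is established.

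**Conclusion.** The point holds as a minor defect of wording. Read literally, the follow-up rule produces dates that the trial's own record contradicts: about 50% of year-only follow-up visits if visits centre on their due dates and due dates are even over the year, and 25 to 75% across the extremes of early and late attendance. Where such a visit sets the DFS censoring date, the patient is censored 6 months early on average (3 to 9), of which about 1.5 to 2 months follow from ignoring the year when visits are centred on the due date.

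The effect on the trial is likely very small. It cannot be sized from the documents, because the number of year-only dates is not given. No effect on the log-rank test or hazard ratio is shown. The misdirected end-of-study cap is a separate slip that does not depend on how the year rule is read.

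**What to change.** 1. In the follow-up row for day and month missing, impute the later of the window lower bound and 1 January of the recorded year. This keeps the SAP's conservative convention and matches the 1 January rule for events. In the example above the visit would be dated 1 January 2013. If the whole window lies after the recorded year, the later-of rule would still give a wrong year; query the visit, or use 1 January of the recorded year.
2. In the exceptions of the follow-up row, replace the therapy stop date with the imputed follow-up examination date, so that the end-of-study cap applies to the variable being imputed.
3. In the therapy table, state when the due date and when 1 July applies. If the due date is used, restrict it to the recorded year.

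The cost is a few lines of SAP text and a short programming change before the analysis. No new data are needed. A count of year-only last visits by arm would show whether the matter has any practical weight.

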### 3.1.3. Stratification errors

Stratification errors defined as different values in the stratification factors compared between the randomization system and actual patient values from the electronic case report forms (eCRF) will be tabulated.

### 3.1.4. Original eCRF pages and amended eCRF pages

If different data were entered on the same data field on the original eCRF page and on the amended eCRF page, the data of the amended eCRF will be chosen and the data on the original eCRF will be discarded.

## 3.2. Types and time points of analyses

According to the protocol, the final analysis of the study should take place after a follow-up of 10 years for each patient. End of 2016 similar studies with prolonged endocrine therapy were presented to the scientific community. At this time, the required number of events was long since been reached. Therefore, the ABCSCG presidium decided in January 2017 to submit an abstract for the presentation at the San Antonio Breast Cancer Symposium (SABCS) in December 2017 based on an advanced analysis. The final analysis should take place approximately after 1 additional year. AstraZeneca agreed to these changes in April 2017.

### 3.2.1. Interim analysis

After recruitment of two thirds of the required number of patients an interim analysis will take place. A significance level of 0.001 will be used, according to the guidelines of Geller and Pocock (1987). If an unexpectedly high effect of the therapy should occur, the study can be terminated early.

### 3.2.2. Advanced analysis

The advanced analysis for the presentation at SABCS 2017 will be based on the cleaned data with cutoff date June 30th, 2016.

### 3.2.3. Final analysis

The final analysis will be performed after the last visit of each patient occurring until June 30th, 2017 and subsequent data cleaning.

## 3.3. Definition of populations for analyses

### 3.3.1. Per-protocol (PP) population

Primary endpoint analysis will be based on the PP; that is, all patients who were randomized, signed the Informed Consent, comply with inclusion and exclusion criteria and have had at least one follow-up examination after randomization and who survived without recurrence for two years. All subjects will be analyzed according to the therapy arm to which they have been

randomized. Subjects who terminate the study before their scheduled final study visits will be censored.

### 3.3.2. Intention to Treat (ITT) population

Secondary endpoint analyses and all sensitivity analyses (including sensitivity analyses for the primary endpoint) will be based on the ITT population; that is, all patients who were randomized and signed the Informed Consent. All subjects will be analyzed according to the therapy arm to which they have been randomized. Subjects who terminate the study before their scheduled final study visits will be censored.

### 3.3.3. Safety (SAF) population

Safety analyses will be based on the SAF population and include all enrolled and treated patients. Hence, all patients who were randomized and received at least one dose of study treatment.

## 3.4. **Description of study population**

The description of the study population is based on the ITT population.

### 3.4.1. Disposition of patients

Recruitment, discontinuation from study including reasons for discontinuation, as well as patient disposition and discontinuation from treatment including reasons for discontinuation will be summarized overall and by treatment arm.

### 3.4.2. Important Protocol Deviations (IPDs)

IPDs include inclusion and exclusion criteria, as well as selected variables related to additional relevant screening assessments, study treatment administration/dispensation, concomitant medication, primary endpoint, study treatment/randomization, study procedures/assessments, withdrawal/termination criteria and safety reporting. The IPDs are defined in a separate document listing all IPDs, their classification and additional details. IPDs will be summarized in total and by treatment arm.

### 3.4.3. Baseline demographic and disease characteristics

Demographic and tumour characteristics data at baseline will be summarized descriptively per treatment arm and in total. Demographic and anamnestic data at baseline include age, tumour stage, nodal status, tumour grade, hormone receptor status (estrogen and progesterone), type of surgery, prior radiotherapy, prior chemotherapy and type of prior endocrine therapy.

## 3.5. Primary endpoint evaluation

### 3.5.1. Primary endpoint

Disease-free survival (DFS) is defined as the time from randomization or from two years after randomization (depending on the type of analysis, see below) to the earliest occurrence of loco-regional recurrence, distant recurrence, contralateral new breast cancer, second cancer or death, from any cause. Patients who have not had a disease recurrence or died will be right-censored at the date of their last assessment of their DFS status.

### 3.5.2. Efficacy analysis for primary endpoint

For the primary endpoint, a 2-sided log-rank test (unstratified) will be used to test for differences between 2 additional years anastrozole versus 5 additional years anastrozole at an overall alpha level of 0.05.

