10.2. Stratification and randomisation

Patients who meet the inclusion and exclusion criteria will be randomised by telephone message in the ABCSG randomisation centre

Tel. no.: [REDACTED] 8
or
[REDACTED]

Randomisation times:
Mon – Thu 8:30 am – 12:00 pm and 1:00 pm – 3:00 pm
Fri 8:30 am – 2:00 pm

using a computer program and in accordance with the adaptive Pocock and Simon (1975) randomisation method. This computer-aided randomisation procedure ensures that the marginal distribution of the characteristics of the stratification criteria is the same in both treatment groups. The randomisation date is recorded. For randomisation, the personal patient data and stratification criteria must be announced.

The patient number received from the randomisation centre consists of two elements:

- A four-digit number for sequential numbering of patients
- A letter code indicating the treatment arm:
 - A: For Arm A, 2 years of therapy with anastrozole (Arimidex®)
 - B: For Arm B, 5 years of therapy with anastrozole (Arimidex®)

Stratification criteria:

The following stratification criteria are used:

1. PT stage:
 - PT1 (≤ 2 cm)
 - PT2 ($> 2-5$ cm)
 - PT3 (> 5 cm)

2. PN stage:
 - No LN metastasis
 - 1-3 LN metastasis
 - 4-9 LN metastasis
 - ≥ 10 LN metastasis

3. Adjuvant primary hormone therapy:
 - 5 years anti-oestrogen
 - 2 years + anti-oestrogen + 3 years anastrozole
 - Comparable endocrine therapy

4. Adjuvant chemotherapy:
 - Anthracycline-containing CT
 - Taxane-containing CT
 - Other CT
 - No CT

5. Study participation:
 - Study 8 from ABCSG
 - Study 9 from ABCSG
 - None

6. Receptor status:
 - ER+PgR+
 - ER+PgR-
 - ER-PgR+

In principle, the result of the examination of the biochemical receptor determination should override that obtained by immunohistochemistry.

7. State:
 - Vienna
 - Lower Austria
 - Burgenland
 - Styria
 - Carinthia
 - Upper Austria
 - Salzburg
 - Tyrol
 - Vorarlberg

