10.4. Efficacy analysis

The final analysis is carried out according to the intent-to-treat principle of all randomised patients who meet the inclusion and exclusion criteria, have at least one follow-up examination after randomisation, and have survived for 2 years relapse free. They will be assigned to the group into which they were randomised regardless of whether they actually received the therapy or which one.

The graphical representation of the therapeutic effect on the primary and secondary target variables (DFS, overall survival and occurrence of secondary cancers, contralateral breast cancer and fractures) is based on the survival functions according to Kaplan and Meier (1958). The differences between the two study arms are tested using the log-rank test (Mantel (1966)).

In addition, the regression model according to Cox (1972) is used in an exploratory way to examine whether the consideration of additional prognostic factors modifies the results of the log-rank tests. This takes into account primarily the stratification criteria of the randomisation but also other prognostic factors. Differences in the therapy are quantified using hazard ratios (relative mortality risk during therapy compared with the control group). In addition, possible interactions of the therapy with other prognostic factors are examined. In the event of significant interactions, subgroup analyses are carried out.

All calculations are performed using the statistical software SAS® (Statistical Analysis Software; version 8) and all tests are two-tailed, where $p \leq 0.05$ is deemed statistically significant.

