#### *Types of analyses for the primary endpoint*

##### Main analysis:

Start time for DFS: 2 year after randomization

Population: PP

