##### Sensitivity analysis 2:

Start time for DFS: randomization

Population: ITT

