### 3.6. Secondary endpoint evaluation

All secondary endpoint analyses will be based on the ITT population. For all secondary endpoints, 2-sided log-rank tests (unstratified) will be used to test for differences between 2 additional years anastrozole versus 5 additional years anastrozole at an overall alpha level of 0.05. No multiplicity adjustment will be applied for the secondary endpoints.

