## 3.8. Exploratory analyses

Exploratory analyses will be based on the ITT population.

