### 3.8.1. Subgroup analyses

DFS will be analyzed using Cox proportional hazard models within each of following subgroups:

- Age group: age  $\leq$  60, age  $>$  60
- Tumor stage: T1, T2 and T3
- Histological grade: Grade I, Grade II, Grade IIIs
- Hormone receptor status: ER+/PgR+, any negative
- Previous hormone therapy: Tamoxifen, Tamoxifen+AI, AI
- Previous chemotherapy: any chemotherapy, no chemotherapy

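### The log-rank tests use none of the seven minimisation factors, and the only adjusted overall estimate is exploratory and on ITT; a stratified test with a matching hazard ratio is a small, cheap improvement

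*SAP*

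**What the plan says.** Protocol 10.2 allocates patients by Pocock-Simon minimisation on pT, pN, primary hormone therapy, chemotherapy, earlier study participation, receptor status and federal state. It says the procedure "ensures that the marginal distribution of the characteristics of the stratification criteria is the same in both treatment groups". SAP 2.3 lists the same seven factors.

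No planned test uses them. For DFS, SAP 3.5.2 says "a 2-sided log-rank test (unstratified) will be used to test for differences". For the secondary endpoints, SAP 3.6 says "2-sided log-rank tests (unstratified) will be used".

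The main DFS analysis is on the PP set, with "Start time for DFS: 2 year after randomization". Sensitivity analysis 1 changes the population to ITT. Sensitivity analysis 2 also moves the origin: "Start time for DFS: randomization".

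Adjustment appears in two other places:

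- Protocol 10.4 says "the regression model according to Cox (1972) is used in an exploratory way", mainly with the stratification criteria, and says that therapy differences are expressed as hazard ratios.
- SAP 3.8.2 plans multivariable analyses with six of the seven factors plus grade, radiotherapy and age. SAP 3.8 adds: "Exploratory analyses will be based on the ITT population".

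SAP 3.8.1 says "DFS will be analyzed using Cox proportional hazard models within each of following subgroups", but pN is not among the subgroups listed.

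**The concern.** When allocation is balanced on prognostic factors, a test that ignores them is slightly conservative, and the marginal hazard ratio lies a little closer to 1 than the hazard ratio within strata. The plan therefore gives up some precision from data it already holds.

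The second gap is in estimation. SAP 3.5.2 names no hazard-ratio model for the primary endpoint. The adjusted analysis in 3.8.2 names neither a model nor a start time, allows correlated covariates to be dropped in the light of the results, and is on a different population from the main DFS test. The Cox model in SAP 4.2.3.2 contains treatment-by-previous-therapy interactions, so it does not give an overall adjusted effect either. A reader of the final DFS result would have no pre-specified adjusted hazard ratio that matches the test.

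**Working it through.** **The plan's own figures (Protocol 10.1).** The hazard ratio is ln(0.916)/ln(0.937) = 1.348, which agrees with the stated 1.35. Schoenfeld's formula for 85% power at two-sided 5% with 1:1 allocation (assumed) is 4(1.960 + 1.036)²/(ln HR)². It gives 399 events at HR 1.35 and 403 at 1.348; Freedman's gives 405 and 409. The stated 433 is not reproduced; at 433 events power would be 87.0 to 87.7%. With 3,325 patients, 5 years of accrual and 2.7 further years, about 410 events are expected and power is 85.2 to 85.7%, so the 85% itself stands. The 433 is a separate matter and does not affect this point.

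**Prognostic strength of nodal status.** Protocol 2.3.1 gives 5-year event risks of about 10% (node-negative) and 17 to 19% (node-positive):

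- ln(0.83)/ln(0.90) = 1.77
- ln(0.81)/ln(0.90) = 2.00

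These risks come from two different trials. DFS in this trial also counts second cancers and all deaths (Protocol 8.1). One scenario therefore lets the nodal effect act on only half of the events.

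**Simulation.** 3,500 patients are minimised on all seven factors. The 5% with an event before year 2 are removed, leaving 3,325. DFS runs from year 2 with exponential hazards, 3-year DFS of 0.937 in Arm B, and the Arm A hazard multiplied by 1.348. The strata are pN (0, 1-3, ≥4) by pT (1, 2-3). Both tests were applied to the same 20,000 trials per scenario; the standard error of the power difference is 0.04 to 0.14 points. Results at the design timeline (9.7 years, 400 to 409 events):

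| Prognostic effects | Unstratified power (%) | Stratified power (%) | Gain (points) |
|---|---|---|---|
| Nodal HR 1.77 on half of events | 85.1 | 85.2 | 0.1 (SE 0.06) |
| Nodal HR 1.77 on all events | 85.0 | 85.2 | 0.2 |
| Nodal HR 2.00 | 84.7 | 85.1 | 0.4 |
| Assumed pN 1.6/2.6/3.5, pT 1.5/2 | 84.3 | 84.9 | 0.7 |
| Assumed strong pN 2/4/8, pT 1.8/3 | 81.9 | 84.0 | 2.1 |

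Gains are taken before rounding.

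**At the cut-offs in SAP 3.2:**

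| Cut-off | Events (strong case) | Unstratified power, % (strong) | Gain, points (strong) |
|---|---|---|---|
| 30 June 2016 | 529-535 (517) | 92.2-93.1 (90.2) | 0.0-0.5 (1.9) |
| 30 June 2017 | 572-579 (557) | 94.1-94.8 (92.2) | 0.0-0.4 (1.6) |

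Schoenfeld's formula agrees: 93.3% at 535 events and 94.8% at 575. If the 7% drop-out is read as annual, unstratified power at the design timeline is 77.4 to 78.3% and the gain is 0.0 to 0.8 points.

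**Estimate and error rates.** The unstratified Cox hazard ratio averages 1.34 to 1.35 (strong case 1.33). The stratified one averages 1.35, against a true within-stratum value of 1.348. Stratified 95% intervals cover 94.9 to 95.5%. Rejection under the null is 4.7 to 5.1% unstratified (strong 4.2%) and 4.8 to 5.1% stratified (strong 4.7%).

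**Cross-check.** A simpler simulation (3,325 patients, arms balanced within strata, 6,000 trials per scenario, somewhat different assumed effects) gave 84.4% to 84.9%, 84.8% to 85.3% and 84.0% to 84.5%. That is about half a point each time.

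**Why not all seven factors.** Full crossing gives 3 × 4 × 3 × 4 × 3 × 3 × 9 = 11,664 cells. Under assumed level shares it keeps about 62% of the log-rank information, and power at 433 events would fall from 87.5% to about 69%. pN alone keeps 99.9%.

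**The case against.** The plan contains no error here. The protocol names the log-rank test, and the SAP states openly that it is unstratified. With the only prognostic input in the documents, diluted because DFS counts second cancers and all deaths, the gain cannot be distinguished from zero. The larger gains rest on assumed pN gradients and pT effects. Adjustment is already planned in SAP 3.8.2, with more covariates than the two proposed here. The population mismatch is narrow: the secondary endpoints (SAP 3.6) and the advanced analysis (SAP 4.2.1) are on ITT, as is the adjusted model, and the protocol's own Cox analysis sits under the set that the SAP calls PP. Finally, the trial is open-label and SAP 3.2 says the event target had long been passed, so replacing the primary test now could look driven by the data.

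Most of this stands, and it limits the point to a modest one. It does not supply what is missing: a pre-specified adjusted hazard ratio, with fixed strata, on the population and start time of the main DFS test. The risk of a late change is a reason to add the stratified analysis as a sensitivity analysis, not a reason to omit it.

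**Conclusion.** The point holds as a low-priority improvement. Type I error is not inflated and the planned 85% power is not lost. Stratifying by collapsed pN and pT is worth 0.1 to 0.7 power points at the design timeline, about 2 if prognosis is much steeper than the documents suggest, and close to nothing if pN and pT predict only part of the DFS events. The more useful gain is the matching adjusted hazard ratio for the main DFS analysis.

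The sizes rest on assumptions that are not in the documents: pN shares of 67/24/6/3% and pT shares of 70/27/3%, level shares of the other five factors (given no prognostic effect), all pT effects and graded pN effects, the one-half dilution, a biased-coin probability of 0.8, and 7% drop-out read as annual. Raising the node-positive share to 45% changes the 0.2-point gain to 0.3 and leaves the 0.7-point gain at 0.7.

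**What to change.** In SAP 3.5.2, and likewise in 3.6, specify a log-rank test stratified by pN (0, 1-3, ≥4) and pT (1, 2-3), using the values held in the randomisation system. Report the hazard ratio with 95% CI from a Cox model stratified by the same six strata, on the same population and start time as the corresponding main analysis.

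- If this can be fixed before anyone sees results by arm, make the stratified test primary and keep the unstratified test as supportive.
- Otherwise keep the unstratified test as primary and add the stratified test and hazard ratio as a pre-specified sensitivity analysis on the main-analysis population.

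Do not cross all seven factors.

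The cost is a few lines of text and one extra model, with no new data. Making the stratified test primary departs from the test the SAP now names. In either case the collapsed strata need a short justification; under the assumed shares, the smallest stratum has about 15 expected events at the design timeline.
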